13.2.4.1 Day 30 Blood Sample Collection

All subjects will be required to provide a blood sample at Day $30 \ (\pm 10 \ days)$ for analysis of SCr. This blood sample can be drawn during the Day $30 \ visit$ or by a visiting phlebotomist if the subject is unable to return to the study site during the Day $30 \ follow-up$ window. Every effort will be made to collect a blood sample at Day $30 \ for$ all subjects. No imputation will be made for missing values.

13.3 Detail of Baseline Assessments and Procedures

13.3.1 Physical Examination

A complete physical examination, including weight and height, will be conducted at baseline and at the 30-day follow-up. This will include a general physical assessment of the major body systems evaluating any new clinically significant abnormalities within the following: general appearance, skin, head/eyes/ears/nose/throat, neck, heart, lungs, abdomen, extremities, neurological, back/spinal, and lymph nodes. This includes worsening of baseline conditions.

In addition, abbreviated physical examinations will be conducted every day during the 14-day active study period.

The investigator may perform additional unscheduled examinations to manage or evaluate a suspected AE as clinically necessary. The timing and scope of additional unscheduled examinations should be determined by the nature and severity of the AE being evaluated. In the case of suspected cardiac, intestinal or other ischemia, examination of the subject by a physician should be completed on an emergency basis (generally within 15 to 30 minutes). For suspected cardiac ischemia, examination should include assessment of vital signs, cardiac and pulmonary auscultation, and evaluation of jugular venous pressure by clinical examination and other components as determined by the physician's clinical judgment. For suspected cardiac ischemia, site must perform an ECG and cardiac enzymes (high sensitivity troponin) at the time of assessment and 3 hours later. Subjects with suspected intestinal ischemia should undergo careful examination of the abdomen to evaluate for the presence of diffuse or focal tenderness, rebound, or acute abdomen with diffuse rigidity. For suspected intestinal ischemia, venous (blood) lactate levels must be drawn and compared to baseline levels. Further investigations should be carried out based on clinical practice. All subjects should have evaluation of the skin of the trunk and extremities for mottling, cyanosis, blanching or pallor.

Clinically relevant abnormalities found upon physical examination will be reported and analyzed as AEs.

13.3.2 Electrocardiogram

A 12-lead electrocardiogram (ECG) will be performed at baseline. Clinically relevant abnormalities found will be reported on the medical history page. The investigator may perform additional unscheduled examinations to manage or evaluate a suspected AE as clinically necessary. Clinically relevant abnormalities found upon subsequent ECGs will be reported and analyzed as AEs. The dates of all subsequent ECGs will be reported on the ECG eCRF.

13.3.3 Child-Pugh Scores

Child-Pugh score will be calculated at baseline and entered in the eCRF.

13.3.4 Vital Signs

The proposed post-study-drug time points for collection of systolic/diastolic blood pressure and heart rate are based on PK data from the OT-0401 and REVERSE clinical trials. The 5 (± 2) min and 2 (± 0.25) h time points roughly coincide with peak plasma concentrations of terlipressin and lysine-vasopressin respectively. Refer to Section 13.4.1.

13.3.5 Assessment of Multi-Organ Dysfunction

With the advancement in intensive care medicine, multiorgan dysfunction syndrome (MODS) has replaced the term multiorgan failure since the completion of the REVERSE study. According to Al-Khafaji et al, 2015, MODS describes a continuum with incremental degrees of physiologic derangements in individual organs; a process rather than a single event. Alteration in organ function can vary widely from a mild degree of organ dysfunction to completely irreversible organ failure.

Multi-organ failure or dysfunction, a hallmark of acute on chronic liver failure (ACLF), common in the study patient population, is defined and quantified by the original CLIF-SOFA score or its simplified version Chronic Liver Failure Consortium (CLIF-C) Organ Failure score (Arroyo et al, 2015). The scoring system has been developed and validated for predicting mortality in patients with ACLF (Jalan et al, 2014).

Table 13–2 CLIF-C Organ Failure Score

Organ System	Score = 1	Score = 2	Score = 3
Liver, bilirubin (mg/dL)	< 6	6 to ≤ 12	> 12
Kidney, creatinine (mg/dL)	< 2	2 to < 3.5	\geq 3.5 or renal replacement
Brain, grade (West-Haven)	0	1 to 2	3 to 4
Coagulation, INR	< 2.0	2.0 to < 2.5	≥ 2.5
Circulation, MAP (mm Hg)	≥ 70	< 70	Vasopressors
Respiratory PaO ₂ /FiO ₂	> 300	\leq 300 and $>$ 200	≤ 200
or SpO ₂ /FiO ₂	> 357	$> 214 \text{ and} \le 357$	≤ 214

Source: Arroyo et al, 2015.

Abbreviations: FiO_2 = fraction of inspired oxygen; INR = international normalized ratio; MAP = mean arterial pressure; PaO_2 = partial pressure of arterial oxygen; SpO_2 = pulse oximetric oxygen saturation.

During baseline information collection and adverse event reporting, the investigators are required to record the actual organs involved in MODS (ie, other organs involved in MODS in addition to the baseline hepatic and renal dysfunction, and the severity of dysfunction in each organ involved), as well as MODS, itself, as a disease state. The use of the simplified version CLIF-C Organ Failure scoring system in documenting MODS organ involvement and MODS severity is strongly encouraged. Assessment of MODS will be detailed in the Site/Investigator Study Manual.

13.4 Detail of Safety Assessments and Procedures

13.4.1 Vital Signs

Vital sign measurements will be recorded at baseline (with the physical examination), during study drug administration, at the end of treatment, and at the Day 30 follow-up.

Systolic and diastolic blood pressure and heart rate will be recorded at baseline, and pre-dose and post-dose at 5 minutes (\pm 2 min) and 2 hours (\pm 0.25h) for every dose.

Body temperature, respiratory rate, and pulse oximetric saturation (SpO₂) will be recorded once daily at baseline and during study drug administration.

13.4.2 Encephalopathy Score

Clinically detectable encephalopathy is to be assessed prior to study drug administration and daily during study drug administration using the clinical criteria described in Table 13–3.

Table 13–3 West Haven Criteria for Semiquantitative Grading of Mental State

Grade 1	Trivial lack of awareness.
	Euphoria or anxiety.
	Shortened attention span.
	Impaired performance of addition.
Grade 2	Lethargy or apathy.
	Minimal disorientation for time or place.
	Subtle personality change.
	Inappropriate behavior.
	Impaired performance of subtraction.
Grade 3	Somnolence to semi-stupor, but responsive to verbal stimuli.
	Confusion.
	Gross disorientation.
Grade 4	Coma (unresponsive to verbal or noxious stimuli).

Source: Ferenci et al, 2002.

13.4.3 Model for End-Stage Liver Disease Score

Model for end-stage liver disease (MELD) scores will be calculated by the sponsor based on SCr, bilirubin and INR values at baseline and treatment Days 1, 3, 7 and treatment termination.

13.4.4 Adverse Events

All adverse events will be assessed and recorded beginning with study drug administration until 7 days after discontinuation of study drug. Adverse events considered serious will be assessed and recorded until 30 days after discontinuation of study drug; excluding deaths, which will be collected up to 90 days after the first dose of study drug.

Those events that are serious in nature must be reported to the sponsor or its designee for safety reporting in an expedited manner (see Section 14 for definitions and reporting requirements).

The adverse event collection schedule for the proposed study is adopted from the previous clinical studies in the same patient population and for the same drug. The time frames for collecting various types of adverse events are defined to focus on the collection of safety information pertinent to the study subjects in the proposed study, as the target patient population has an extensive health background and existing medical conditions.

13.4.4.1 Adverse Events of Special Interest

Based on its known mechanism of action and pharmacodynamics effects, terlipressin treated subjects may develop central or peripheral ischemia and signs/symptoms of pulmonary congestion including bronchospasm, wheezing, etc. To better characterize and help conduct a thorough safety analysis for these events, additional information will be requested from study sites for subjects who report AEs of select MedDRA preferred terms. These AEs will be considered as adverse events of special interest and will include abdominal pain, chest pain or dyspnea/wheezing/bronchospasm/pulmonary edema. Sites will be required to complete an additional Adverse Events of Special Interest eCRF page and provide information, ie, characteristics of the event (location, time course, aggravating/relieving factors) as well as clinical laboratory and other investigations including radiologic imaging studies conducted in relation to the reported event.

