5.3.3 Safety

Most subjects in both treatment groups in the OT-0401 and REVERSE studies experienced at least 1 adverse event (AE), which is expected given the high incidence of disease-related events in this severely ill patient population. The most commonly observed adverse reactions in terlipressin-treated subjects were abdominal pain and diarrhea (refer to Table of Adverse Drug Reactions in the Investigator's Brochure). Less common adverse reactions with clinical significance that were reported in terlipressin-treated subjects include: wheezing, respiratory failure, peripheral ischemia manifested as skin necrosis, peripheral coldness, livedo reticularis and Raynaud's phenomenon; intestinal ischemia including ischemic colitis; myocardial ischemia including myocardial infarction. The safety characteristics of terlipressin in the 2 studies were consistent with its vasoconstrictor mechanism of action. None of the events leading to discontinuation of terlipressin in either study were fatal and all resolved afterwards. Refer to the Investigator's Brochure for further details.

The safety characteristics of terlipressin observed in the 3 randomized, controlled trials is consistent with the established safety profile of terlipressin from 30 years of clinical experience, as captured in the literature and post-marketing data from the World Health Organization (WHO) database. There were no new, unusual or unexpected AEs observed in the clinical studies compared to the published data.

For detailed terlipressin safety risk profiling, please refer to the Investigator's Brochure.

In general, terlipressin has a well-established safety profile in the treatment of patients with HRS Type 1. The safety risks are predictable and recognizable. The adverse drug reactions can be readily managed and reversed by terlipressin dose reduction or interruption in hospital-care settings.

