Note: Use of short-term (less than 2 weeks) oral neomycin for acute encephalopathy is acceptable.

- 7. Estimated life expectancy of less than 3 days.
- 8. Superimposed acute liver injury due to drugs (eg, acetaminophen), dietary supplements, herbal preparations, viral hepatitis, or toxins (eg, *Amanita* toxin with mushroom poisoning, carbon tetrachloride), with the exception of acute alcoholic hepatitis.

Note: subjects meeting criteria for drug, dietary supplement or herbal preparation induced liver injury (http://livertox.nih.gov/; Chalasani et al, 2014) should be excluded

- 9. Proteinuria greater than 500 mg/day.
- 10. Evidence of obstructive uropathy or parenchymal renal disease on ultrasound or other imaging.
- 11. Tubular epithelial casts, heme granular casts, hematuria or microhematuria (greater than 50 red blood cells per high power field in the absence of recent catheterization) on urinalysis.

Note: Urine sediment examination is required to exclude presence of heme granular casts and other clinically significant casts.

- 12. Subjects known to be pregnant; all women of child-bearing age and potential must have a negative pregnancy test.
- 13. Severe cardiovascular disease, including, but not limited to, unstable angina, pulmonary edema, congestive heart failure requiring increasing doses of drug therapy, or persisting symptomatic peripheral vascular disease, myocardial infarction or stable chronic angina within the past 12 months, or any other cardiovascular disease judged by the investigator to be severe.
- 14. Current or recent (within 4 weeks) RRT.

- 15. Participation in other clinical research involving investigational medicinal products within 30 days of randomization.
- 16. TIPS within 30 days of randomization.
- 17. Use of vasopressors (eg, norepinephrine, epinephrine or vasopressin, dopamine or other vasopressors) of at least 3 consecutive days within prior 14-day screening period. Patients receiving a vasopressor other than midodrine within 24 hours of qualifying SCr are excluded, ie, a 24-h washout is required prior to enrollment.
 - *Note*: Patients receiving midodrine and octreotide may be enrolled. Midodrine and octreotide treatment must be stopped prior to randomization.
- 18. Known allergy or sensitivity to terlipressin or another component of the study treatment.

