10.3.2 Dose Modifications

- If SCr has decreased, but by less than 30% from the baseline value on Day 4 after a minimum of 10 doses of study drug, the dose of study drug will be increased to 2 mg every 6 hours (± 30 minutes) (8 mg/day).
- The dose should not be increased in subjects with coronary artery disease or in the setting of circulatory overload, pulmonary edema, or bronchospasm.
- If dosing is interrupted due to an adverse event, study drug may be re-started, at the discretion of the investigator, at the same or lower dose as per protocol (refer to Section 10.3.2.1). Study drug will not be restarted if dosing was interrupted due to cardiac ischemia or mesenteric ischemia.
- If in the investigator's judgment, a dose increase is not advisable or otherwise justified in the individual subject, the reason(s) for not increasing the dose of study drug will be documented on the electronic case report form (eCRF).

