10.3.2.1 Management of Adverse Events

With the exception of presumed cardiac or intestinal ischemia, the initial management of AEs may include dose reduction or temporary interruption of study drug dosing. After dose interruption, study drug may be restarted at a reduced dose of 0.5 mg or 1 mg every 6 to 12 hours. At the discretion of the investigator, the dose may then be increased to the previous dose level. Careful assessment of concomitant medications and treatment (particularly albumin dosing) and their potential relationship to the AE should be undertaken and adjusted as per standard of care and investigator discretion. If possible, study drug dosing should be restarted promptly and/or maintained at usual or reduced dosing particularly for the first 4 days of study drug administration. Investigators are encouraged to discuss any dosing questions with the Medical [contact] Management of Fluid Overload

Volume overload in this context refers to intravascular volume overload manifested as pulmonary congestion or overt pulmonary edema. Subjects with increasing dyspnea, cough, orthopnea, or tachypnea should be carefully evaluated for evidence of pulmonary edema (physical examination and, as judged by the investigator to be indicated, chest X-ray or other investigations). In subjects with fluid overload, especially those with respiratory events

(dyspnea, respiratory distress), careful assessment of concomitant albumin and temporary albumin dose reduction or discontinuance may be the most appropriate initial management. Judicious, short term use of temporary diuretic therapy as per standard of care may be undertaken at the discretion of the investigator in some subjects in whom a response to diuretic therapy is expected. If fluid overload requiring intervention persists after these initial measures, further management should include dose reduction or temporary interruption of study drug dosing as above.

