14.2 Collection of Adverse Events/Serious or Unexpected

Any AE occurring prior to signing the ICF should be considered medical history or a pre-existing condition and will be collected on the Medical History eCRF.

All AEs will be assessed and recorded beginning with study drug administration until 7 days after discontinuation of study drug and at each evaluation. Adverse events considered serious will be assessed and recorded until 30 days after discontinuation of study drug, excluding deaths, which will be collected up to 90 days after the first dose of study drug.

The investigator will collect and record all necessary data including investigations that were performed for any AE of special interest, ie, an ischemic abdominal event, ischemic cardiac event, or bronchospasm-related respiratory event.

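### Peripheral ischemia is named as a terlipressin effect, but it is missing from the special-interest event lists and from the list that blocks the Day 4 dose increase

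*Combined protocol and SAP*

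**What the plan says.** **The hazard is recognized.** Section 5.3.3 lists, among the less common reactions of clinical significance, "peripheral ischemia manifested as skin necrosis, peripheral coldness, livedo reticularis" and Raynaud's phenomenon. Section 13.4.4.1 says, from the drug's mechanism, that "terlipressin treated subjects may develop central or peripheral ischemia". Section 8.4 excludes subjects with "persisting symptomatic peripheral vascular disease". Section 13.3.1 asks for an urgent physician examination when any ischemia is suspected, not only cardiac or intestinal, and for a check of the skin of the trunk and extremities.

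**The lists that trigger extra data collection.** Section 13.4.4.1: "These AEs will be considered as adverse events of special interest and will include abdominal pain, chest pain or dyspnea/wheezing/bronchospasm/pulmonary edema". Section 14.2 asks for all necessary data on "any AE of special interest, ie, an ischemic abdominal event, ischemic cardiac event, or bronchospasm-related respiratory event".

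**The dosing rules.** Under Section 10.3.2, a subject whose creatinine has fallen by less than 30% from baseline on Day 4, after at least 10 doses, has the dose raised to 2 mg every 6 hours. The exceptions are: "The dose should not be increased in subjects with coronary artery disease or in the setting of circulatory overload, pulmonary edema, or bronchospasm". An investigator who judges an increase inadvisable may withhold it and record why. The same section adds: "Study drug will not be restarted if dosing was interrupted due to cardiac ischemia or mesenteric ischemia". Section 10.4 requires a permanent stop for the same two kinds of ischemia. Other adverse events fall under Section 10.3.2.1, which allows dose reduction or interruption and says: "If possible, study drug dosing should be restarted promptly and/or maintained at usual or reduced dosing". The synopsis repeats the dose-increase, no-increase, no-restart and stop rules.

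**The concern.** The special-interest page exists because the drug can cause central or peripheral ischemia, yet its triggers reach only the central kind and the respiratory events. The page asks for location, time course, aggravating and relieving factors, laboratory results and imaging. That detail is what would separate ischemic coldness or discoloration from other causes in very sick patients with cirrhosis. If the page is not triggered, the detail may not be collected and cannot be fully recovered later.

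The dosing gap concerns subjects' safety. Bronchospasm, pulmonary edema, circulatory overload and coronary artery disease each block the Day 4 increase by an explicit rule. New peripheral ischemia, a recognized effect of the same vasoconstrictor, does not. Whether the dose goes up then depends on each investigator's judgment.

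**Working it through.** The plan states no figure on this point, so there is nothing to reproduce. The check sets the sections side by side and then adds one illustration of size.

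**Step 1. Where each kind of event is covered**

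| Provision | Cardiac | Abdominal | Respiratory or fluid | Peripheral |
|---|---|---|---|---|
| Named as a drug effect (5.3.3, 13.4.4.1) | yes | yes | yes | yes |
| Extra-page triggers (13.4.4.1) | chest pain | abdominal pain | dyspnea, wheezing, bronchospasm, pulmonary edema | none |
| Special-interest list (14.2) | yes | yes | bronchospasm-related | none |
| No-increase list (10.3.2) | coronary artery disease | none | circulatory overload, pulmonary edema, bronchospasm | none |
| No restart (10.3.2) and permanent stop (10.4) | yes | mesenteric | none | none |

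Abdominal ischemia needs no entry in the no-increase list, because mesenteric ischemia already ends dosing. Respiratory and fluid events carry no permanent stop but do block the increase. Peripheral ischemia is the only column with no entry below the first row.

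**Step 2. What the Day 4 rule does**

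Starting dose: 1 mg every 6 hours = 4 × 1 = 4 mg/day. Increased dose: 4 × 2 = 8 mg/day. Take a subject with new peripheral signs who is still on drug on Day 4, has had at least 10 doses, and whose creatinine has fallen by less than 30%. This subject meets the condition for the increase and none of the listed exceptions. Only the investigator's documented judgment prevents it. A subject whose creatinine is at or above baseline on Day 4 should stop study drug under Section 10.4, so the gap does not reach that group.

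**Step 3. How likely it is that a case occurs**

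Inputs: n = 200 terlipressin subjects (Section 15.3.1). The rate r of peripheral ischemia is an assumption, because the documents give none.

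Expected cases = n × r. Chance of at least one = 1 − (1 − r)^n.

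| Assumed rate | Expected cases | Calculation | Chance of at least one |
|---|---|---|---|
| 0.5% | 1 | 1 − 0.995^200 | 63% |
| 1% | 2 | 1 − 0.99^200 | 87% |
| 2% | 4 | 1 − 0.98^200 | 98% |

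These are chances of any case in the arm. The number who also have signs by Day 4, fall in the creatinine range for an increase, and are not held back by the investigator must be smaller. The documents do not give what is needed to size it.

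**The case against.** The strongest reply is that little is lost. Section 13.3.1 provides urgent examination, a skin and extremity check and daily abbreviated examinations, and clinically relevant findings are reported as adverse events. Section 13.4.4 has all adverse events recorded to 7 days after the last dose, and Sections 15.1 and 15.3.6.4 classify and tabulate them. Skin necrosis or livedo is visible and largely identifies itself, whereas abdominal pain and dyspnea need work-up. A safety board, a 24-hour hotline and the investigator's freedom to stop any subject (Section 8.5) add protection. All of this stands, and it keeps the point small. It does not explain why a page introduced for peripheral ischemia is not triggered by it.

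A second reply is that the trigger list in Section 13.4.4.1 may be open-ended, since it refers to selected coded terms without listing them all. That is possible. The list in Section 14.2 also differs from it, by not naming pulmonary edema. But both lists omit peripheral events, and nothing in the visible text tells a site to complete the page for them.

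A reader might also infer three stronger things that the documents do not support:

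- **That an ischemia count will be too low.** No pooled ischemia count and no safety test or interval is planned in the visible text. Any such undercount belongs to an analysis that the plan does not specify.
- **That dosing is restarted and doubled by default after peripheral ischemia.** After an interruption, Section 10.3.2.1 allows restart at 0.5 or 1 mg every 6 to 12 hours, then a return only to the previous dose at the investigator's discretion. The Day 4 increase is a separate rule with its own conditions and a documented opt-out.
- **That a permanent stop is plainly missing.** Section 5.3.3 says that none of the events that led to discontinuation in the two earlier placebo-controlled studies was fatal, that all resolved, and that reactions respond to reduction or interruption. Bronchospasm and pulmonary edema carry no permanent stop either. Graded handling is defensible.

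**Conclusion.** The gap is real but limited. The protocol names peripheral ischemia as a drug effect and gives it as a reason for the special-interest page, then leaves it out of both special-interest lists and out of the list that blocks the Day 4 increase. The result is that the extra page is not required for these events, and that a move from 4 to 8 mg/day is the written default unless the investigator documents otherwise.

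At assumed rates of 0.5%, 1% and 2%, at least one terlipressin subject would have such an event with a chance of 63%, 87% and 98%. These figures rest wholly on the assumed rates and on 200 subjects in the arm. They show that the gap could plausibly matter for a handful of subjects. They do not show harm, and nothing here touches the efficacy conclusions or the planned adverse event tables. It is a cheap improvement to safety rules and data capture.

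**What to change.** 1. Add signs of peripheral ischemia to the no-increase list in Section 10.3.2 and in the synopsis.
2. Add the peripheral terms of Section 5.3.3 (skin necrosis, peripheral coldness, livedo reticularis, Raynaud's phenomenon) to the page triggers in Section 13.4.4.1, and peripheral ischemic events to the list in Section 14.2.
3. Have the sponsor decide, and state, whether skin necrosis or other ischemic tissue injury should also carry a permanent stop and no restart (Sections 10.3.2, 10.3.2.1 and 10.4). This is a clinical threshold, and leaving milder signs under reduction or interruption would be reasonable.

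The cost is a phrase in a few places and some trigger terms on an existing page. A few subjects with mild, reversible signs would stay at 1 mg every 6 hours and might lose some benefit. For subjects already treated, the page could be completed only by query.
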